6.2. Permanent System Implant

Implantation of the neurostimulation system will be performed according to the sites standard operating procedures and should be consistent with instructions in the IFU. It should be performed after the baseline assessments and no later than 60 days from the enrollment visit. If it has not occurred within 60 days after Enrollment, the subject will be withdrawn (Section 5.5). Following system implantation, the stimulator will be activated and programmed by trained personnel either during post-operative recovery or at an office visit in accordance with the physician's and hospital's standard operating procedures. The subject's spinal cord stimulator will be programmed according to the most recent Abbott programming guidance. After programming, the subject will receive a patient programmer and will be instructed on how to use the system to relieve their pain.

The investigator or delegate will instruct the subject on use of the charger, including weekly charging after the initial wound healing period.

Clinical Investigation Plan

A charging plan for the patient should satisfy the following criteria:

- First battery charge prior to attending the 2-week follow up visit
- Weekly battery charge after 2 weeks

The following information will be collected at the permanent system implant:

- Neurostimulation system device information
- Lead type(s) and location
- Programming parameters subject is using at the end of device activation
- All serious adverse events including deaths (if applicable)
- Non-serious adverse events related to device, procedure, stimulation, charging, or MRI (if applicable)
- Withdrawal (if applicable)
- Device deficiency (if applicable)
- Additional Surgery (if applicable)

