3.4 Descriptive Performance Endpoints or Additional Data

Descriptive Endpoints

The descriptive endpoints will be analyzed using the methods defined in 2.2 based on implanted population defined in 2.1. The descriptive endpoints will be analyzed at baseline and at 6 weeks if applicable.

Descriptive endpoints include:

- Patient satisfaction
- Patient experience with charging
- NRS score change
- PROMIS-29 change
- Charging history

The following charging history will be summarized using the methods defined in 2.2

- Time between implant and first charging session in days
- Number of charging sessions
- The rate of charging sessions per follow-up week
The numerator will be the total number of charging sessions. The denominator will be the total follow-up duration (in weeks) from the date of first charging started to the last follow-up date
- Average duration of charging (in hours) per charging session
- Average charging interruptions per charging session
- Rate of charging sessions with Overheat protection events, which is defined as total number of sessions with overheating protection flag/total number of charging sessions
- The average percent of battery at end of the charging sessions per charging session

- Stimulation programs used
- Stimulation programs available

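### SAP 3.4 starts the weekly charging rate at each subject's first charge, so never-chargers have no rate and a late starter's uncharged weeks are left out

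*SAP*

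**What the plan says.** SAP 3.4 summarises charging history "based on implanted population defined in 2.1". That definition is redacted in the public text, and nothing here turns on it. Three of the listed measures matter most:

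- Time to first charge: "Time between implant and first charging session in days".
- The session count: "Number of charging sessions", with no condition attached, so it can be 0.
- The weekly rate: "The numerator will be the total number of charging sessions", and "The denominator will be the total follow-up duration (in weeks) from the date of first charging started to the last follow-up date".

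The other SAP 3.4 charging measures (duration, interruptions, overheat flags, battery level at the end of charging) are taken per session. Battery consumption in SAP 3.4.1 needs two consecutive sessions.

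SAP 2.2.1 summarises continuous variables by number of observations, mean and SD, with quartiles, range and a confidence interval where applicable. It has no method for censored times. SAP 2.7 rules out imputation but names only the confirmatory endpoint. No visible text says how a subject with no charging session enters these summaries.

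Protocol 6.2 sets two criteria for a charging plan: "First battery charge prior to attending the 2-week follow up visit" and "Weekly battery charge after 2 weeks". Protocol 6.3 puts the 2-week visit at days 10 to 14 and the 6-week visit at days 30 to 45. No SAP measure is tied to either criterion.

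**The concern.** The study's objective is to show that the system works as intended in clinical use, and Protocol 1.1.2 names the charger among the new components. A subject who cannot or does not charge, or who starts weeks late, is among the most informative on that question.

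The rate as defined describes charging only after it has begun. A never-charger contributes nothing to it, whether it is computed per subject (no value) or pooled (nothing added to numerator or denominator). The session count cannot fully stand in for a rate, because it is not adjusted for follow-up that may end anywhere from day 30 to day 45. With 20 planned subjects, each one is 1/20 = 5% of the data.

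**Working it through.** The plan gives no expected charging rate, so there is no figure to reproduce. The check applies the SAP formulas to assumed patterns.

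**Inputs from the documents:** the rate formula and time-to-first-charge definition (SAP 3.4), the charging plan (Protocol 6.2), the visit windows (Protocol 6.3) and 20 planned subjects (SAP 1.3).

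**Assumptions:** last follow-up on day 42, the charging days below, the numbers of late and never-chargers, and a mean of 12 days to first charge among those who charge. The documents give none of these.

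**Step 1: one subject.** SAP rate = sessions ÷ ((last follow-up day − first charge day)/7). The fixed-start rate divides sessions on or after day 14 by (42 − 14)/7 = 4 weeks.

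| Charging days | SAP rate | SAP rate without the first session | Fixed start, day 14 |
|---|---|---|---|
| 14, 21, 28, 35, 42 (on plan) | 5/4 = 1.25 | 4/4 = 1.0 | 5/4 = 1.25 |
| 35, 42 (late) | 2/1 = 2.0 | 1/1 = 1.0 | 2/4 = 0.5 |
| none | undefined | undefined | 0/4 = 0 |

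The late starter's 2.0 is inflated by counting the session that starts the clock, which is a separate matter. With that session removed, the late and on-plan subjects both show 1.0, so the rate cannot tell them apart. From implant, the late starter's rate would be 2/6 = 0.33, but that counts two weeks before weekly charging was due, so day 14 is the fairer comparison. A first charge on the day of last follow-up gives a zero denominator.

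**Step 2: a cohort of 20** (assumed: 16 on plan, 2 starting on day 35, 2 never charging).

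- Sessions: 16×5 + 2×2 = 84. SAP weeks: 16×4 + 2×1 = 66.
- SAP pooled rate: 84/66 = 1.27, against 100/80 = 1.25 if all 20 are on plan.
- Without each charger's first session: (84 − 18)/66 = 1.0, against (100 − 20)/80 = 1.0.
- Fixed start at day 14: 84/(20×4) = 1.05, against 1.25.
- Mean time to first charge: (16×14 + 2×35)/18 = 16.3 days on n = 18, against 14.0 on n = 20.
- Mean sessions: 84/20 = 4.2, against 5.0.

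The SAP rate does not fall although 4 of 20 subjects are off plan. The other two measures do move.

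**Step 3: never-chargers and time to first charge.** With k never-chargers among 20, the SAP mean covers only the 20 − k who charged and stays at 12.0 days. Counting the others to day 42 gives ((20 − k)×12 + k×42)/20:

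- k = 1: (228 + 42)/20 = 13.5
- k = 2: (216 + 84)/20 = 15.0
- k = 3: (204 + 126)/20 = 16.5

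These are lower bounds, because the true times lie beyond day 42.

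**The case against.** Starting the clock at first charge is a defensible choice. Protocol 6.2 places weekly charging after initial wound healing, and Protocol 15.2 warns against charging while staples are in place. A rate from first charge answers how often subjects charge once they have begun, and delay is reported separately. This stands, and it is a reason to keep that rate as a supplement.

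The neighbouring measures also limit the damage. The late subject above shows 35 days to first charge and 2 sessions, against 14 days and 5 sessions on plan. A never-charger shows as 0 sessions and as a smaller n. A reader might infer that a late starter looks fully compliant, or that a never-charger vanishes from the report. The documents support neither: both remain visible in the session count, and the SAP labels no measure as compliance. Nor does time to first charge begin at the first charge; it runs from implant and is undefined only if no charge occurs.

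There are other routes to detecting a charging failure: the 2-week check that the charging plan is understood, device deficiency reporting, charging-related adverse events and the patient charging experience item. The data are descriptive, with no threshold. All this lowers the stakes. It does not repair the rate, and a reduced n does not say why values are missing.

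**Conclusion.** The point holds for the rate and for the measures that depend on having charged. Followed as written, SAP 3.4 gives a never-charger no rate instead of 0, leaves a late starter's uncharged weeks out of the rate, and averages time to first charge over chargers only. This follows from the stated denominator, not from redacted text.

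In the illustrations, the late starter's rate is 1.0 per week where 0.5 describes days 14 to 42, and the mean time to first charge is understated by at least 1.5, 3.0 or 4.5 days (13.5, 15.0 and 16.5 minus 12.0) for 1, 2 or 3 never-chargers. The sizes rest entirely on assumed patterns; if everyone charges on plan, the effect is nil. A reader might also infer from 2.0 against 1.25 that the choice of clock start rewards delay. That rise comes from counting the opening session; without it, the rate fails to react to delay but does not reward it.

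The change should be made, in proportion to descriptive data. The confirmatory safety endpoint is unaffected.

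**What to change.** Amend SAP 3.4 for the implanted population, with subjects lacking a downloaded log counted and reported separately.

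1. Compute the rate as sessions on or after day 14 divided by weeks from day 14 to the last log date, with 0 for subjects with no session. Count separately any subject whose log ends by day 14, since no denominator exists. The rate from first charge may stay as a supplementary measure, labelled as conditional on having started.
2. Report the number of subjects with no session. Report the number and percentage with a first charge before the 2-week visit, and with weekly charging after 2 weeks, as Protocol 6.2 sets out, with the Clopper-Pearson intervals already provided in SAP 2.2.2. The SAP should state how each criterion is read from the log. Precision will be low: 4 of 20 off plan is 20%, with an interval of 5.7% to 43.7%.
3. Summarise time to first charge with never-chargers censored at the last log date, for example by a Kaplan-Meier median. Otherwise, state clearly that the mean covers only those who charged.

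The cost is SAP wording and a little programming on data already collected. The downside is a possibly less favourable charging rate.

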3.4.1 Additional Analyses

Battery consumption per day will be summarized using the method defined in 2.2.1.

The battery consumption per day is calculated as

$$\frac{\sum(\text{Battery (\%)} \text{ usage between two consecutive charging sessions})}{\sum(\text{days between the two consecutive charging sessions})}$$

For example, the first charging is on Mar 27th, 2021, the battery (%) is 85% at the end of the charging session. The next charging is April 10th, 2021 and the battery is 29% at beginning of charging. The battery usage is calculated as 85%-29%=56%. There are 14 days between the two charging sessions.

Other additional analysis may be needed for exploratory purposes.

4.0 DOCUMENTATION AND OTHER CONSIDERATIONS

[REDACTED]

[REDACTED]

[REDACTED]

Statistical Analysis Plan

5.0 ACRONYMS AND ABBREVIATIONS

AE	Adverse Event
CEC	Clinical Events Committee
CIP	Clinical Investigation Plan
CLBP	Chronic Low Back Pain
CMM	Comprehensive Medical Management
CRF	Case Report Form
CT	Computed Tomography
DMP	Data Management Plan
EC	Ethics Committee
ECG	Electrocardiogram
EDC	Electronic Data Capture
FAS	Full Analysis Set
FDA	U.S. Food and Drug Administration
GCP	Good Clinical Practice
HIPPA	Health Insurance Portability and Accountability Act
ICF	Informed Consent Form
IFU	Instructions for Use
IRB	Institutional Review Board
MHRA	Medicines and Healthcare Products Regulatory Agency
MRI	Magnetic Resonance Imaging
NRS	Numerical Rating Scale
ODI	Oswestry Disability index
PCS	Pain Catastrophizing Scale
PGIC	Patient Global Impression of Change
PRO	Patient Reported Outcome
PROMIS	Patient-Reported Outcomes Measurement Information System
SAE	Serious Adverse Event
SCS	Spinal Cord Stimulation
UADE	Unanticipated Adverse Device Effect
US	United States

Statistical Analysis Plan

